## 7. Selection of Subjects

Consecutive eligible patients will be recruited at the outpatient clinic in the participating center by the involved physician (surgeon). All patients fulfilling the above-mentioned criteria will be informed about the study by the physician. After consent is given, central data acquisition will take place web-based and patients will be treated according to the study protocol.

### 7.1 Consent

Potential participants will be counselled by a member of the research team directly involved with the study and who hold good clinical practice certification. Patients will be provided with written information and the consent form at the time of counselling with an opportunity to ask any questions. All patients participating in the study must hold capacity- this is an inclusion criteria and the absence of it an exclusion criteria.

## **7.2 Inclusion criteria**

- Patient scheduled for elective laparoscopic cholecystectomy
- Patient age  $\geq$  18 years
- Patient able to give consent to the procedure

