## 1. Study summary

Study Title	Safety of laparoscopic ChOlecystectomy performed by Trainee surgeons with different CHolangiographic techniques (SCOTCH)
Internal ref. no. (or short title)	SCOTCH study
Study Design	Multicenter prospective interventional trial
Study Participants	Patients
Endpoints	Primary endpoints Time to reach CVS with the utilisation of three different intraoperative imaging modality during LC performed by ST
Summary of eligibility criteria	
Inclusion Criteria
 
 
- Patient scheduled for elective laparoscopic cholecystectomy
 
- Patient age <math>\geq</math> 18 years
 
- Patient able to give consent to the procedure
 
 
Exclusion Criteria
 
 
- Open cholecystectomy
 
- Emergency laparoscopic cholecystectomy
 
- Allergy towards iodine, lohexol or indocyanine green
 
- Liver or renal insufficiency
 
- Thyrotoxicosis
 
- Pregnancy or lactation
 
- Legally incompetent for any reason
 
- Withdrawal of inclusion consent at any time
 
- Age outside inclusion range
 

Arms of the study	
Group CVS-WL (control group): the CVS is achieved in white light, without the utilization of an intraoperative imaging technique. CVS in white light was selected as the control group since it constitutes the actual recognized standard in clinical practice.
 
Group IOC: the CVS is achieved with the help of intraoperative cholangiography
 
Group NIR-C: the CVS is achieved with the help of near-infrared fluorescence cholangiography

Version and date of protocol amendments	Vers. n.1.1- 15/11/2020
Clinicaltrials.gov Registration number	NCT04863482

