#### 4. Background

Laparoscopic cholecystectomy (LC) gained popularity among general surgeons in 1990s and rapidly become one of the most commonly performed procedures in digestive surgery [1, 2], with more than one million cholecystectomies being performed in the United States per year [3]. LC remains also one of the most commonly performed procedure by general surgeons during the training period [4, 5].

Even if previous report LC cases performed by surgical trainees (ST) are not associated with higher operative morbidity [6], the length of operative time is significantly increased when compared with that of LC cases performed by attending surgeons, due, most of all, to difficulties in identifying the anatomical structures [7, 8], and this sometimes leads to an attending surgeon taking away the case from the trainee.

Furthermore, despite the fact that LC has proven to be a safe procedure, the rate of common bile duct (BDI) injury still remains unacceptably high even in the hands of minimally invasive trained surgeons [9] ranging from 0.2 to 1.5% in individual reports [10, 11-14], much higher than initial reports [14, 15], associated with significant morbidity and mortality, lower quality of life and increased costs, related to additional health care measures, loss of work days, and insurance claims [2,10, 16, 17]. Way et al reported that, in 97 % of cases, non-technical errors, predominantly relating to perceptual errors, in which the operator was led to make false assumptions regarding the position of the bile duct in relation to the anatomy at hand, were at the root cause of the injury. [18] From these observation many of the existing recommendations to avoid BDI insist on the importance of the establishment of the critical view and understanding the relevant anatomy, aided by adequate retraction and visualization. [19]

The correct identification of Calot's triangle, sometimes hard even in expert hand, may be particularly challenging for ST leading at those misidentification of the structures that are the most frequent causes of BDI during LC as previously stated. As a matter of fact, the most frequent site of CBD injury is below the bifurcation of the right and left hepatic ducts (65 %), and once anatomic confusion has led the surgeon astray, injury tends to occur in relatively predictable locations along the biliary tree [4]

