## **6. Study objectives**

### **6.1 Primary Outcomes**

The primary objective is to compare NIFC, IOC and CVS-WL for identification of the junction between the cystic duct, the common hepatic duct and the CBD during LC performed by general surgery trainee always supported by an expert surgeon. The technique will be considered successful when the CVS will be achieved. The time to achieve the CVS will be recorded by an independent surgeon who will be present in the operative room during the procedure.

The definition of trainee will be on the number of the procedures performed before the beginning of the study. Surgeons who performed less than 30 procedures before the beginning of the study, since learning curve studies have determined the steep portion to consist of 10 to 30 operations [40–43]. The operating surgeon will complete a structured questionnaire focusing on anatomical identification of the bile ducts immediately after each operation (**Appendix A**) and a more generic

questionnaire on task load. (**Appendix B**) The surgeon's satisfaction score will be given on a subjective visual analogue scale ranging from 1 to 5 (1 = not satisfied, 5 = extremely satisfied). (**Appendix C**)

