## **7.3 Exclusion criteria:**

- Open cholecystectomy
- Emergency laparoscopic cholecystectomy
- Allergy towards iodine or indocyanine green
- Liver or renal insufficiency
- Thyrotoxicosis
- Pregnancy or lactation
- Legally incompetent for any reason
- Withdrawal of inclusion consent at any time
- Age outside inclusion range

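### The restriction to trainee-performed operations is not carried into eligibility or the recorded data, so an expert's takeover before CVS counts as a trainee success and cannot be identified afterwards

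*Protocol*

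**What the plan says.** The trainee restriction stands in the title, the endpoint and the objective. The protocol summary (section 1) gives the primary endpoint as "Time to reach CVS with the utilisation of three different intraoperative imaging modality during LC performed by ST". Section 6.1 describes operations "during LC performed by general surgery trainee always supported by an expert surgeon" and sets the limit for a trainee at fewer than 30 earlier procedures.

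The operational sections do not repeat it. The only condition on the operation in section 7.2 is "Patient scheduled for elective laparoscopic cholecystectomy"; the other two items are age and capacity to consent. Section 7.3 excludes, for example, "Emergency laparoscopic cholecystectomy", but names nothing about the operator. Section 7 says "Consecutive eligible patients will be recruited at the outpatient clinic".

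On takeover, section 4 reports that trainees operate more slowly, mainly because the anatomy is hard to identify, and that "this sometimes leads to an attending surgeon taking away the case from the trainee". Section 6.1 treats a technique as successful when CVS is reached and has an independent surgeon in the room record the time. Section 6.3 lists thirteen parameters, including the time to CVS. Section 9 analyses by intention to treat.

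**The concern.** The trial asks which technique best helps a trainee identify the anatomy. When the expert takes the instruments before CVS because the trainee cannot find the structures, the technique has failed for that trainee. It is the event most relevant to the question, and the protocol expects it to occur.

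Followed as written, the success rule records that event as a success, with a time that mixes trainee and expert work. The protocol also gives reasons why takeover might differ between groups. Section 4 says that supervising a trainee's dissection towards CVS is difficult without visual landmarks, that intraoperative cholangiography (IOC) can be hard to teach, and that fluorescence cholangiography has promise as a teaching tool. If so, the result could be distorted on exactly the point the study is meant to settle. No later analysis can repair this if the takeover was never recorded.

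**Working it through.** **1. Where the operator is fixed, and where not.**

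- Fixed: the title, the primary endpoint in section 1, and the objective and trainee definition in section 6.1.
- Not fixed: sections 7, 7.2 and 7.3.
- Not recorded: none of the thirteen items in section 6.3 is the operator, the operator's earlier case count or a takeover. The Appendix A questions have no such item. Appendices B and C are not visible in the text at hand, but their titles concern task load and satisfaction.
- The independent surgeon is asked for the time, not for who is operating.

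**2. One taken-over case, followed through.** A trainee starts, cannot identify the structures, the expert takes over, and CVS is reached. Section 6.1 makes this a success. Section 6.3 stores one time to CVS. Section 9 keeps the case in its group. The operating surgeon fills in the questionnaires, and it is not stated whether that is now the trainee or the expert. The record looks the same as that of a trainee who finished unaided.

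**3. Effect on the success rate.** Let S be the share of cases in which the trainee reaches CVS, f the share taken over before CVS, and c the share of those in which the expert then reaches CVS.

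Recorded success = S + f × c

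The protocol gives no f or c. Assume c = 1 and no other failures, so S = 1 − f. With f = 20% in one group and 5% in another:

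- trainee success: 80% and 95%, a difference of 15 points;
- recorded success: 0.80 + 0.20 = 100% and 0.95 + 0.05 = 100%, a difference of 0.

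For scale, the first calculation in section 9.1 assumes 80% against 90%, a difference of 10 points. If f and c are equal in two groups, both rates are overstated by the same amount and their difference is unchanged.

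**4. Effect on mean time.** Let R be the recorded time of a taken-over case divided by the time had the trainee finished it. Assume f = 5–20% and R = 0.5–0.9, and taken-over cases of average length.

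Relative change in a group's mean = −f × (1 − R)

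- Smallest: 0.05 × 0.1 = 0.5%. Largest: 0.20 × 0.5 = 10%.

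If the techniques have equal trainee times, the recorded imaging/control ratio is [1 − f_imaging(1 − R)] / [1 − f_control(1 − R)]:

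| Takeover, control / imaging | R = 0.5 | R = 0.9 |
|---|---|---|
| equal | 1.00 | 1.00 |
| 20% / 5% | 0.975/0.900 = 1.083 | 0.995/0.980 = 1.015 |
| 5% / 20% | 0.900/0.975 = 0.923 | 0.980/0.995 = 0.985 |

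**5. Is a taken-over case short?** Suppose such cases are h times as long as average in a trainee's hands, a share k of that time has passed at takeover, and the rest runs at a factor s. Recorded time relative to the average case = h × (k + (1 − k)s). With h = 1.3–1.6, k = 0.3–0.6 and s = 0.5–0.7 (assumptions):

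- lowest: 1.3 × (0.3 + 0.7 × 0.5) = 0.845;
- highest: 1.6 × (0.6 + 0.4 × 0.7) = 1.41.

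The case is shorter than if the trainee had finished it (0.65 to 0.88 of that time), but it may still be longer than the average case.

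**The case against.** **The protocol does restrict the operator.** A reader might infer from sections 7.2 and 7.3 that operations done wholly by the expert are admitted and counted as trainee results. The documents do not support that. The title, section 1 and section 6.1 limit the study to trainee-performed operations, and section 7 says patients are treated according to the protocol. Such a case lies outside the study. What stands is that the limit is not carried into eligibility or data collection, so a departure from it would not show.

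**The direction for time is not established.** A reader might also infer that takeover shortens the primary time, that the technique with most takeovers gains most, and that a false-positive rate can be put on this. Section 4 supports slower trainees only for total operative time and gives no minutes. Harder cases are the likely ones to be taken over (step 5). Section 8 starts the IOC time at application of the grasper, after the cystic duct is dissected, but starts the other two at initial dissection; an early takeover in the IOC group could fall outside the timed interval. Any false-positive rate would need an assumed takeover difference, time saving and standard deviation. And if technique causes a difference in takeover, the techniques already differ for trainees, so that is not a clean null. This objection stands.

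**Some of this may sit elsewhere.** Section 6.3 is a summary list, the web-based form is not shown, and the handling of takeover could be left to a statistical analysis plan. This stands in part: the form may hold such a field. But the success definition is in the protocol and is silent on who achieves CVS, and an analysis plan cannot use a variable that was not collected.

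**Conclusion.** The point holds in this form and should be corrected. By the protocol's own rules a takeover before CVS is counted as a trainee success with a completed time, and no listed item identifies it. That conclusion comes from reading sections 4, 6.1, 6.3, 7.2, 7.3 and 9 together and needs no assumed figure.

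The consequence is conditional. If takeover differs between groups, the comparisons of success and of time to CVS are biased. Neither the size nor, for time, the direction can be derived from the documents. The 15-point loss in success and the time ratios of 0.923 to 1.083 illustrate assumed takeover of 20% against 5% and are not estimates. With equal takeover and an equal time ratio R, the ratio of mean times is not affected.

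**What to change.** - **Section 7.2:** add that the LC is planned to be performed by a trainee as defined in section 6.1.
- **Section 6.3:** add the operator's earlier LC count and takeover by the expert before CVS (yes/no, and when). The independent surgeon who already times the case can record it.
- **Section 6.1:** define success as CVS achieved by the trainee, with takeover before CVS counted as not achieved.
- **Time to CVS:** do not treat a taken-over case as an ordinary completed time. One option is to give it the worst rank in the Wilcoxon comparison that section 9 already allows, with the time as recorded in a sensitivity analysis. A t-test on means cannot carry a worst rank, so the Wilcoxon test would then have to be the primary one.

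None of this touches when an expert should take over; it only records and counts that it happened.

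The cost is one eligibility line, one or two data fields and the reworded definitions, with no extra staff. The price in interpretation is that time becomes a composite of speed and completion by the trainee, and the result depends partly on the decision of a supervisor who knows which technique is in use. The report should therefore give takeover by group alongside the primary result.

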## **7.3 Exclusion criteria:**

- Open cholecystectomy
- Emergency laparoscopic cholecystectomy
- Allergy towards iodine or indocyanine green
- Liver or renal insufficiency
- Thyrotoxicosis
- Pregnancy or lactation
- Legally incompetent for any reason
- Withdrawal of inclusion consent at any time
- Age outside inclusion range

## **8. Study procedures**

### **Critical view of Safety(CVS)**

The CVS has 3 requirements. First, the triangle of Calot must be cleared of fat and fibrous tissue. It does not require that the common bile duct be exposed. The second requirement is that the lowest part of the gallbladder be separated from the cystic plate, the flat fibrous surface to which the non peritonealized side of the gallbladder is attached. The cystic plate, which is sometimes referred to as the liver bed of the gallbladder, is part of the plate/sheath system of the liver. The third requirement is that 2 structures, and only 2, should be seen entering the gallbladder. Once these 3 criteria have been fulfilled, CVS has been attained). The rationale of CVS is based on a 2-step method for ductal identification that was and continues to be used in open cholecystectomy. First, by dissection in the triangle of Calot, the cystic duct and artery are putatively identified and looped with ligatures. Next, the gallbladder is completely dissected off the cystic plate, demonstrating that the 2 structures are the only structures still attached to the gallbladder. Time consumption and includes the period from the initial dissection and the obtaining of an acceptable view according to the previously described criteria in order to safely transect the cystic duct.

### **Intraoperative cholangiography (IOC)**

IOC is performed after dissection of the cystic duct in a standardised manner, by cannulation of the cystic duct with a catheter using either a Kumar or Olsen grasper. Leakage is controlled by injecting saline prior to injection of iodine contrast means, according to the centre usual habits. A mobile X-ray C-arm system is used, and the monochrome X-ray image is shown on a separate screen. After satisfactory identification of the extra-hepatic biliary ducts, the intraoperative cholangiography is discontinued and the gallbladder is removed in a standardised manner. Time consumption includes

the period from application of the Kumar/Olsen grasper until it is removed again after obtaining a satisfactory cholangiogram and the cystic duct is transected.

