## 6.3 Evaluated parameters

- i) Age
- ii) Sex
- iii) ASA scores
- iv) Preoperative work up
- v) Type of procedure (CVS-WL, NIFC, IOC)
- vi) Operative parameters (operative time, intraoperative complications)
- vii) BDI (according to the ATOM, Stasberg's and LAU classification [44-46] **Appendix E**)
- viii) How the BDI was diagnosed intraoperatively
- ix) Duration of cholangiography
- x) Time needed to obtain a CVS
- xi) Post-operative outcomes (post-operative complications, late complications, need of readmission, length of hospital stay)
- xii) Surgeons' ease at performing the procedure (questionnaire on identification of anatomical structures, NASA task load test)
- xiii) Surgeons' satisfaction (visual analog scale)

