### **Near infrared cholangiography (NIR-C)**

NIFC is performed injecting intravenously, 2.5-7.5 mg of indocyanine green (0.2 mg/kg) at the admission of the patients into the hospital, in patients admitted the same day of surgery, and at least 45 mins before the acquisition of the images. Indocyanine green rapidly binds to plasma proteins and is exclusively and entirely excreted by the hepatic parenchymal cells into the bile, starting within a few minutes after injection. During dissection, the fluorescence imaging mode is used when needed until critical view of safety is obtained. Before division of any tubular structure, the fluorescence imaging mode is routinely used again, and fluorescent angiography is performed by re-injecting the same dose of indocyanine green as initially used. After division of the cystic duct and artery, the fluorescence imaging mode is applied again to check for bile leakage. Time consumption includes the period from the initial dissection and the obtaining of an acceptable CVS and transect the cystic duct.

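### Time to CVS, the primary endpoint in the study summary, has no common start and stop across the three arms, and the only interval defined for IOC is not a time to CVS

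*Protocol*

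**What the plan says.** The study summary (Section 1) gives a single primary endpoint: "Time to reach CVS with the utilisation of three different intraoperative imaging modality during LC performed by ST". Section 6.1 adds how it is captured, "The time to achieve the CVS will be recorded by an independent surgeon who will be present in the operative room during the procedure", but gives no start or stop event.

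The only start and stop events are in Section 8, one per technique, each introduced as time consumption:

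- White light: the interval "includes the period from the initial dissection and the obtaining of an acceptable view according to the previously described criteria". The sentence then gives safe transection as the purpose of the view.
- NIR-C: "Time consumption includes the period from the initial dissection and the obtaining of an acceptable CVS and transect the cystic duct".
- IOC: "the period from application of the Kumar/Olsen grasper until it is removed again after obtaining a satisfactory cholangiogram and the cystic duct is transected". The same subsection places this step in the operation: "IOC is performed after dissection of the cystic duct in a standardised manner".

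Section 6.3 lists "Duration of cholangiography" (item ix) and "Time needed to obtain a CVS" (item x) as separate parameters and defines neither.

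**The concern.** A time endpoint can be compared between arms only if the clock starts and stops at the same events in each. In Section 8, IOC has a different start from the other two arms, and its stop is tied to a cholangiogram and transection rather than to CVS. Part of any difference between IOC and the other arms would then come from the definition and not from the technique. Such an offset is systematic, so enrolling more patients does not dilute it; it makes a false difference more likely to reach significance.

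Section 5.3 says the trial is meant to propose a standard technique for trainee-performed surgery, so a difference created by the clock would feed directly into that recommendation. The loss is also permanent: a start time not noted in theatre cannot be reconstructed at analysis.

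**Working it through.** **Step 1. The three clocks side by side (Section 8).**

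| Arm | Start | Stop | Stop refers to CVS? |
|---|---|---|---|
| White light | initial dissection | acceptable view under the three criteria | yes |
| NIR-C | initial dissection | acceptable CVS and, as worded, cystic duct transected | yes, plus a later step |
| IOC | grasper applied, after cystic duct dissection | grasper off after a satisfactory cholangiogram, cystic duct transected | no |

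White light and NIR-C share a start; only IOC starts elsewhere. If the NIR-C clock does run to transection, it also takes in the repeat fluorescence imaging and angiography that Section 8 requires before any tubular structure is divided. The white-light clock has no counterpart to these.

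**Step 2. What the IOC clock measures.** Let D be the time from first dissection to grasper application, C the grasper-on to grasper-off time, and T the transection time. The protocol gives no value for any of them.

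- Written IOC clock: C + T.
- Common clock from first dissection to readiness to transect: D + C. Written minus common = (C + T) − (D + C) = T − D, so the written clock is too short whenever the untimed dissection lasts longer than the transection.
- Common clock from first dissection to CVS, if CVS is complete before the grasper goes on: D. Written minus common = C + T − D. The omitted dissection pulls the figure down, while the cholangiography and transection pull it up.

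The omission always shortens the IOC time by D. The net error depends on D, C and T and on the stop point intended. Section 8 says only that the cystic duct has been dissected before IOC, not that all three CVS criteria are already met, so some dissection may also fall after the grasper is applied.

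**Step 3. Could Section 6.3 repair this?** If the IOC interval is item ix, item x still needs a start and a stop in the IOC arm, and none is given anywhere.

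**Step 4. Scale (illustration only).** The protocol states no mean, SD or target difference for time, so there is no plan figure to reproduce. Suppose true times are equal and the clocks alone create a net offset of d SD between two arms of n patients each. With a two-sided 0.05 test (Section 9), the chance of a significant result is approximately

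Φ(d/√(2/n) − 1.96) + Φ(−d/√(2/n) − 1.96).

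Example, n = 60 and d = 0.25: √(2/60) = 0.1826 and 0.25/0.1826 = 1.369, so Φ(−0.591) + Φ(−3.329) ≈ 0.278.

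| Net offset d (assumed) | n = 60 | n = 300 |
|---|---|---|
| 0.25 SD | 0.278 | 0.865 |
| 0.50 SD | 0.782 | >0.99 |
| 0.75 SD | 0.984 | >0.99 |
| 1.00 SD | >0.99 | >0.99 |

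The nominal rate is 0.05. The group sizes are those in Section 9.1, which were derived for proportions and not for times; they serve here only to give a scale.

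**The case against.** The strongest reply is that the IOC interval was never meant as the primary clock. Grasper-on to grasper-off fits item ix of Section 6.3, time to CVS is item x, and no sentence links the time consumption wording to the endpoint. This is a fair reading, and it means the protocol cannot be said to be biased for certain. It does not rescue the endpoint: the same label supplies the time to CVS in the other two arms, and on this reading the IOC arm has no start or stop at all.

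Second, the NIR-C sentence is ungrammatical and may be a clumsy version of the white-light purpose clause. That stands. The stop difference between white light and NIR-C holds only as worded and is less certain than the IOC problem.

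Third, Section 6.1 frames the primary objective as anatomical identification, with success meaning that CVS is achieved, and Section 9.1 sizes on proportions. The status of time is therefore not consistent across the protocol. Time to CVS is still the only primary endpoint the summary names, and Section 6.1 has it recorded.

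Fourth, definitions are often left to the SAP. Here the protocol itself fixes the intervals, and they must be captured during the operation.

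A reader might also infer that IOC is bound to come out fastest, or that the true ranking will be reversed. The documents do not support that: they give no dissection, cholangiography or transection times, and Step 2 shows that the net sign depends on all three and on the intended stop. Nor do they support the inference that every arm starts at a different step.

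**Conclusion.** The point holds as a defect of endpoint definition: the protocol gives no common start and stop for time to CVS. Either the IOC time omits dissection that the other arms count, which biases it towards looking shorter, or the IOC arm has no defined time to CVS. Neither reading gives a comparable primary endpoint.

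The evidence is firm for the IOC start and for the absence of CVS from the IOC interval. It is weaker for the NIR-C stop, which rests on one poorly worded sentence. The magnitude is unknown. The significance probabilities above depend on assumed offsets in SD units and show only that a moderate offset would matter at the group sizes mentioned. The definition should be settled before any case is timed.

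**What to change.** In Section 8 and the case report form, define one start for all three arms: first dissection of the hepatocystic triangle. Record two stop points in every arm:

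- (a) the three CVS criteria met, used for the primary endpoint;
- (b) readiness to transect the cystic duct after any imaging.

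Both are needed. A stop at CVS alone could leave the cholangiography untimed if CVS is reached before the grasper goes on, whereas (b) captures cholangiography and fluorescence time.

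State who declares each stop, identically in all arms. At present Section 6.1 has the independent surgeon record the time, while Appendix A asks the operating surgeon whether CVS was achieved, and only on the white-light form. The independent surgeon can go on recording the times. Keep grasper-on to grasper-off solely as item ix of Section 6.3.

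The cost is one extra time stamp per case, a revised definition and form, and an explicit rule on who declares CVS. The observer is already in the room.
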